4.0 STUDY DESIGN & METHODS

1. Design

This prospective longitudinal cohort study will evaluate the effectiveness of a quadrivalent HPV VLP vaccine in an HIV-positive cohort of girls and women in multiple centres across Canada.

2. Rationale

This study presents a unique opportunity to understand the long term impact of HPV vaccination in immune compromised women. Our prior study demonstrated that although women and girls living with HIV in Canada have complicated lives and have a high burden of socioeconomic disadvantages, they are very interested and committed to participating in research. This is clearly demonstrated by the degree of engagement of positive women in the National Consensus Statement on Women, Trans People and Girls and HIV Research in Canada. Our study sites across the country have been highly effective at engaging with this challenging population

through their long-standing, dedicated clinics. We have a cohort of over 400 girls and women who continue to live with their HIV disease and will require ongoing specialized HIV care for the rest of their lives. As they are just completing the first protocol out to 24 months and are for the most part still attending for care, with 94% remaining engaged with our study groups. We are confident that we can effectively re-engage them in our follow-up study. It is vital that this study be launched now while most participants are at 24-36 months from vaccine course, and key follow up timed sampling can ascertain the trajectory of antibody responses as well as the course of HPV disease.

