7.2.1 Females aged 11-18 who are pre-menarchal and not sexually active

Adolescents and young women will be offered enrollment in the setting of established and experienced pediatric clinics. There are young girls with HIV infection, primarily perinatally acquired, who may be unaware of their diagnosis and the actual terminology of HIV. This is standard practice for care of children up to age 12 with a complex diagnosis with profound social stigmatization issues.

Those that are aware of the HIV terminology will receive the information and consents with HIV specific information. The term "immunocompromised" has been used in place of HIV in documents and

Research Protocol
Long Term Follow-up Study of CTN 236 - A Study of an HPV VLP Vaccine in a
Cohort of HIV Positive Girls and Women

templates that may be viewed by these young women (e.g. consent forms). Each site may use the standard terminology used at their site.

Those girls and women who are pre-menarchal and not sexually active will not have the same degree of disease endpoint evaluations (i.e. will not have any pelvic examinations or Pap smears until post menarchal and sexually active or at the discretion of the site investigator).

A young subject who originally signed an assent form who becomes menarchal and sexually active will be required to sign a consent form that includes the study genital sampling prior to performing any of these procedures.

7.2.2 **Changes to study procedures in pregnancy**

In the event of pregnancy Pap testing and genital study sampling will continue; however, an Ayre spatula will be used to collect cervical samples in place of the cytobroom until 3 months post-pregnancy.

3. **Summary table of study visits**

| | Visit Window | Ongoing Consent/Assent | Incl/Excl or Contraindication Criteria | Clinical Laboratory Investigations | Study Blood-Work (serology) | Pelvic Exam& Vaginal Sample Collection * | Study Cervical Cytology and HPV DNA * | SAE/Med Hx and Con Med/Exposure Update |
|---------------------|---------------------------------------|------------------------|--|------------------------------------|-----------------------------|--|---------------------------------------|--|
| Month 36 (Visit 8) | First Dose + 36 months (+/- 2 months) | X | X | X | X | X | X | X |
| Month 48 (Visit 9) | First Dose + 48 months (+/- 2 months) | X | X | X | X | X | X | X |
| Month 60 (Visit 10) | First Dose + 60 months (+/- 2 months) | X | X | X | X | X | X | X |

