| Month 72 (Visit 11) | First Dose + 72 months (+/- 2 months) | X | X | X | X | X | X | X |
| Month 84 (Visit 12) | First Dose + 84 months (+/- 2 months) | X | X | X | X | X | X | X |

Research Protocol
Long Term Follow-up Study of CTN 236 - A Study of an HPV VLP Vaccine in a
Cohort of HIV Positive Girls and Women

| | | | | | | | | |
|------------------------|---|---|---|---|---|---|---|---|
| Month 96 (Visit 13) | First Dose + 96 months (+/- 2 months) | X | X | X | X | X | X | X |
|------------------------|---|---|---|---|---|---|---|---|

* Those girls and women who are pre-menarchal and not sexually active will not have any pelvic examinations or Pap smears until post-menarchal and sexually active or at discretion of the site investigator.

Due to variation in duration of time since first dose of vaccine, some subjects are out of window for Month 36 and Month 48, e.g. it has been more than 48 months since first dose of vaccine was received. Therefore, we have extended the study visit timeline up to and including Month 96 post-vaccine, also designated Visit 13. Visits will occur annually until project grant is completed (March 31, 2019).

4. Study Visits

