7.4.2 Study Visit Window

| Interval | Length of interval (months) | Recommended interval between scheduled visits (months) |
|---------------------------------|--------------------------------|--|
| First dose to Month 36/Visit 8 | (36 ± 2) | 12 |
| First dose to Month 48/Visit 9 | (48 ± 2) | 12 |
| First dose to Month 60/Visit 10 | (60 ± 2) | 12 |
| First dose to Month 72/Visit 11 | (72 ± 2) | 12 |
| First dose to Month 84/Visit 12 | (84 ± 2) | 12 |
| First dose to Month 96/Visit 13 | (96 ± 2) | 12 |

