12.1.3 HSV2 Serology Testing

Samples will be sent to the BCCDC Virology research laboratory, Vancouver, BC for analysis. The HerpeSelect ELISA (Focus Technologies) will be used but will employ a high cutoff index value of 3.5, which has been shown to offer improved specificity in the setting of HIV co-infection.^{87,88,89} Previously stored blood will be pulled as per protocol for baseline testing and at each study visit, participants will have serum stored for batched testing of HSV type-specific antibody. After baseline determination of serostatus for all participants, follow-up testing will be performed only on previously seronegative participants to assess for interval seroconversion.

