- d) Predictors of HPV antibody seroresponse in our study population will be identified using logistic regression. This analysis is considered to be of vital importance as other vaccines have been shown to not be effective in subgroups of HIV positive individuals and could permit targeting of the proper population allowing for cost-effective use of this vaccine. The primary predictor of interest is CD4 count and justification for this is based on hepatitis B vaccination data described above. The secondary predictors of interest will include the variables: age, presence and number of strains of HPV, HIV viral load, use of HAART, use of injection drugs, and ethnicity. These predictors were chosen as ones that make the most clinical sense for potent impact on vaccine antibody response.

3. **Exploratory Analyses**

HSV analyses will employ linear or logistic regression models as appropriate, with HSV-2 serostatus as a time- updated primary predictor variable. To address these issues, we will quantify the impact of both incident (acquired within the past year) and prevalent (present at the time of diagnosis) HSV-2 co-infection on each of the primary HPV-related outcomes as described in preceding section (GMT, breakthrough HPV infections, genital tract dysplasia, and external genital warts).

Vaginal Microbiota Analysis. The output of the bioinformatics pipeline, including inventory of unique operational taxonomic unit (OTU) sequences, their taxonomic lineage and abundance, will be used to visualize and characterize the vaginal microbiota. Using various community-level analyses available as packages in R: 133

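### Incident HSV-2 is defined by infection in the past year, but the planned testing cannot date first-visit seroconversions that closely, except roughly for month-36 entrants with a month-24 baseline

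*Combined protocol and SAP*

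**What the plan says.** Section 16.3 (Exploratory Analyses) promises to quantify the impact of "incident (acquired within the past year) and prevalent (present at the time of diagnosis) HSV-2 co-infection" on antibody titre, breakthrough HPV infection, dysplasia and genital warts. The method is one sentence: "HSV analyses will employ linear or logistic regression models as appropriate, with HSV-2 serostatus as a time- updated primary predictor variable".

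Section 12.1.3 describes the testing: "Previously stored blood will be pulled as per protocol for baseline testing and at each study visit" participants have serum stored for batched testing. Once baseline status is known, "follow-up testing will be performed only on previously seronegative participants to assess for interval seroconversion". The month of the stored baseline sample is not given.

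Sections 7.3 and 7.4.2 place the visits at months 36, 48, 60, 72, 84 and 96 from first dose, each within 2 months either way. The Summary allows up to three visits per participant. Section 7.3 adds that "some subjects are out of window for Month 36 and Month 48". The Background (part 10) reports parent-study serology at months 0, 7, 12, 18 and 24.

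**The concern.** The definition of incident infection needs a negative test about a year before the first positive one. At the first follow-up visit, the only earlier test the plan provides is the stored baseline sample, which may be several years old. A participant negative at baseline and positive at that visit cannot be shown to meet the definition. She is not prevalent at baseline either, because she tested negative then. The prevalent class is itself tied to a diagnosis that section 16.3 does not name. The plan has no class for such cases, so the choice would fall to the analyst after the data are seen. Counting them all as incident would mix older infections into the class and blur the contrast that section 16.3 wants to estimate.

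A secondary matter is that a time-updated predictor over up to three visits implies several rows per participant for some outcomes, and section 16.3 names no method for this in the HSV-2 models.

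**Working it through.** The plan gives no sample size or event count for the HSV-2 analysis, so there is no stated figure to reproduce.

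**1. Interval lengths (no rate needed).** Gap = first follow-up visit month minus baseline month, plus or minus 2 months for the visit window. No window is given for the parent-study samples.

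| Baseline | Entry 36 | Entry 48 | Entry 60 | Entry 72 |
|---|---|---|---|---|
| Month 0 | 34-38 | 46-50 | 58-62 | 70-74 |
| Month 12 | 22-26 | 34-38 | 46-50 | 58-62 |
| Month 18 | 16-20 | 28-32 | 40-44 | 52-56 |
| Month 24 | 10-14 | 22-26 | 34-38 | 46-50 |

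Of the 30 pairs of documented baseline month (five) and visit month (six), only month 24 with month 36 is nominally 12 months. The next shortest is 18.

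Later visits fit better. Two consecutive in-window visits are (48-2)-(36+2) = 8 to (48+2)-(36-2) = 16 months apart. With one visit missed, the gap is (60-2)-(36+2) = 20 to (60+2)-(36-2) = 28 months.

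**2. Share of the incident class older than one year, if every first-visit seroconversion is counted as incident.** Assumptions: constant seroconversion rate r per year, visits on schedule, baseline month b, entry month e, v annual visits.

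Share = [1 - exp(-r(e-b-12)/12)] / [1 - exp(-r(e-b+12(v-1))/12)]

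Example: b = 0, e = 36, v = 3, r = 0.03 gives (1 - exp(-0.06)) / (1 - exp(-0.15)) = 0.0582/0.1393 = 42%.

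| r = 3% per year | Entry 36 | Entry 48 | Entry 60 | Entry 72 |
|---|---|---|---|---|
| Month 0, 3 visits | 42% | 52% | 60% | 65% |
| Month 0, 2 visits | 51% | 62% | 69% | 74% |
| Month 24, 3 visits | 0% | 26% | 42% | 52% |
| Month 24, 2 visits | 0% | 34% | 51% | 62% |

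Over r = 1-6% each cell moves by 3 points or less. The full range is 41-76% with a month-0 baseline and 0-64% with month 24.

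**3. Size of the class that can be dated.** Assumptions: 380 attend (close to 94% of 407, from sections 4.0 and 5.0) and 45% are seronegative (from the 55% seroprevalence cited in Background part 6). That gives 380 x 0.45 = 171.

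- Month-0 baseline: 171 x [exp(-re/12) - exp(-r(e+12(v-1))/12)]. At 3%, e = 36, v = 3: 171 x 0.0532 = 9.1. Over entry months 36-72 and two or three visits, the count is about 4-9 at 3%, and about 2-16 over 1-6%.
- Month-24 baseline, all entering at month 36, 3% per year: 171 x [1 - exp(-0.06)] = 10 with two visits and 171 x [1 - exp(-0.09)] = 15 with three.

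**4. Repeated rows.** For an HSV-2 status fixed per participant and an outcome entered at every visit as independent rows, type I error = 2 x [1 - Phi(1.96/sqrt(DE))], with DE = 1 + (v-1) x ICC and an assumed two-sided 5% level. With three visits, DE is 1.2, 1.6 and 2.8 at ICC 0.1, 0.3 and 0.9, giving 7.4%, 12.1% and 24.1%. With two visits the results are 6.2%, 8.6% and 15.5%.

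A simulation (380 participants, 55% seropositive, three visits, 15% outcome, ICC 0.1/0.3/0.6, 3000 replicates) gave 7.8/11.5/17.3% with all rows kept. It gave 5.7/4.6/4.6% when participants left the risk set at their first event.

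**The case against.** The strongest reply is that the plan's own definition excludes the doubtful cases. Someone negative at month 0 and positive at month 36 has not been shown to be infected in the past year, so on a literal reading she is unassigned rather than misclassified. This stands. A reader might infer that half or more of the incident class will be misclassified. The documents do not say that, because the shares above apply only if analysts count every first-visit seroconversion as incident.

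The entry mix is also unknown. Section 4.0 says "most participants are at 24-36 months from vaccine course", but this counts from the vaccine course, while visits are timed from first dose, and section 7.3 has some participants already past months 36 and 48. No single blended percentage can be drawn from this. The baseline month is open too. Interest in peak antibody response (section 3.0) and the covariate list in section 16.2(b), which refers to first vaccination, lean towards an early sample, but neither fixes it.

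Nor does the definition fail at every visit. From the second follow-up visit on, annual testing fits it approximately.

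On repeated visits, a reader might infer that the plan treats rows as independent. It does not say so; naming a regression family does not exclude clustered standard errors. For antibody titre, section 16.2(b) lists HSV-2 as a covariate and section 16.2(c) fits GEE within the HIV-positive cohort, so that outcome may already be covered. Once-per-participant outcomes such as peak antibody, and first-event analyses, need no correction. What remains is HPV detection or dysplasia status entered at every visit. The GEE in 16.2(c) concerns antibody response, and the mixed models in 16.3 concern the microbiota.

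**Conclusion.** The point holds as a minor one. Section 16.3 fixes a definition that the testing in section 12.1.3 cannot support for seroconversions found at the first follow-up visit. The one exception is month-36 entry with a month-24 baseline, and then only to within 10-14 months. The interval lengths follow from the visit schedule alone. The potential contamination (41-76% with a month-0 baseline, 0-64% with month 24) rests on a constant 1-6% annual rate, entry between months 36 and 72, two or three visits, and all first-visit cases being counted as incident.

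The repeated-visit point is secondary. It matters only for outcomes entered at more than one visit per participant, where independent rows would give about 7-24% type I error with three visits at an assumed ICC of 0.1-0.9. The HSV-2 aim is exploratory and the primary antibody result is unaffected.

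**What to change.** - State which stored parent-study sample is the HSV-2 baseline.
- Define incident as seroconversion since a negative test at the preceding annual visit (8-16 months for consecutive in-window visits). If the baseline is month 24, month-24 to month-36 seroconversions also qualify.
- Class every other seroconversion, including those after a missed visit, as acquisition time unknown. Alternatively, analyse the actual interval from last negative to first positive test.
- Define prevalent as seropositive at the named baseline sample, in place of the unspecified diagnosis.
- Where an HSV-2 model uses an outcome recorded at more than one visit per participant, fit it by GEE or a mixed model clustered on participant, with a logit link for binary outcomes.

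This costs SAP wording and minor extra analysis, with no new visits or samples. The downside is a small datable incident class: about 2-16 participants with a month-0 baseline, or about 10-15 at 3% per year with a month-24 baseline and all entering at month 36, on the assumptions above. It may support only counts and intervals rather than a model.

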| Duration of study for each subject | 
Up to 60 months
 
Subjects will participate in up to 3 possible study visits over a total of 5 years. Duration of time since vaccination as part of CTN 236 varies depending on when they were enrolled; therefore, to ensure all subjects are offered participation in the long term follow up, 6 possible visit times have been created.
 |
| Visit schedule | Main Study Procedures (no standard clinical or sub-study procedures) |

| | Informed Consent/ Assent | Health Questionnaire | Study Blood Work | Cytology and HPV DNA & vaginal swabs* | SAE and Con Med Assessment |
|------------------------|-----------------------------|----------------------|------------------|---------------------------------------|----------------------------|
| Month 36 (Visit 8) | X | X | X | X | X |
| Month 48 (Visit 9) | X | X | X | X | X |
| Month 60 (Visit 10) | X | X | X | X | X |
| Month 72 (Visit 11) | X | X | X | X | X |
| Month 84 (Visit 12) | X | X | X | X | X |
| Month 96 (Visit 13) | X | X | X | X | X |

* Those girls and women who are pre-menarchal or never sexually active will not have any pelvic examinations, clinical Pap smears, or study genital sampling until post-menarchal and sexually active.

Complete outline of all procedures found in table 7.3

| | |
|--|---|
| Data collection | Template recruitment documents, consent and source documents will be provided by the Study Coordinating Centre. Source data will be transferred to paper case report forms and sent to the CIHR Canadian HIV Trials Network (CTN) where it will be entered into an electronic database. |
| Monitoring | This study is being conducted according to the following: International Committee on Harmonization (ICH) Guidance Document E6: Good Clinical Practice (GCP): Consolidated Guidelines. Site monitoring will be performed to ensure compliance with the above. |
| Data Safety Monitoring Board (DSMB) | The established CTN data safety monitoring committee with additional expertise in pediatrics and gyne-oncology will provide oversight and monitoring of the conduct of the study to ensure the safety of the subjects. Additionally, the DSMB will ensure the validity and integrity of the study data. |

LIST OF ABBREVIATIONS

| | |
|--------------|---|
| AE | Adverse event |
| AIDS | Acquired immunodeficiency syndrome |
| ART | Antiretroviral therapy |
| ARV | Antiretroviral |
| BCCDC | British Columbia Centre for Disease Control |

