5.0 STUDY COHORT

1. Population

Four hundred and seven (407) HIV-positive girls and women (greater than, or equal to, age 11) attending the HIV treatment clinics in each of the 13 sites across Canada and who have enrolled in the original study “A Study of an HPV VLP Vaccine in a Cohort of HIV Positive Girls and Women (CTN 236)” will be offered participation in the study.

Inclusion Criteria

- Enrolled in CTN 236 study
- Able to give fully informed consent or assent

Exclusion Criteria

- Did not receive at least one vaccination via CTN 236, phase 1
- Cannot provide fully informed consent or assent

2. Delays and contraindications to subsequent study procedures

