notably the BiodiversityR, 134 vegan, 135 and ALDeX2136 packages, we will apply statistical and graphical techniques to identify patterns of bacterial diversity that are associated with HPV infection and disease. Specifically, we will use compositional analysis as implemented in ALDeX2 to test for relationships between specific bacterial taxa and HPV infection and cervical dysplasia in addition to other clinical variables at each time point. Taxa thus identified will be examined for changes in relative abundance across time using mixed-effects models to control for multiple measures on each subject, and comparing to HPV infection status, HPV type and other clinical and HIV correlates. We will also use hierarchical clustering methods to determine if the bacterial communities form identifiable and robust clusters, with particular species occurring more often together. We can then test if these clusters are associated with HPV infection, burden of infection (single vs. multiple types) and evidence of cervical disease using standard statistical tests such as logistic regression and ANOVA. Finally, we will use mixed-effects models to test for changes in bacterial diversity and species richness that are associated with HPV infection, burden of infection (i.e. infection with multiple HPV types) and evidence of cervical disease while controlling for repeated measures on each subject.

HIV and Lower Urinary Tract Symptoms Analysis. Descriptive statistics will be used for baseline patient characteristics. Logistic regression analysis will be performed to determine the effect of: severity of HIV (CD4 count, viral load, AIDS criteria met), current HIV medications, time since HIV diagnosis, and vaginal microbiome on lower urinary tract symptoms, while also considering the effects of age, parity, ethnicity, sexual practices (from various questions in the HPV in HIV questionnaire), history of STI, history of UTI, smoking status, alcohol use, drug use.

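### Microbiota analysis: taxa screened against HPV at each visit are then compared with HPV status in the same data, so second-stage HPV p-values for HPV-selected taxa are too small

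*Combined protocol and SAP*

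**What the plan says.** Section 16.0, Exploratory Analyses, describes two linked steps for individual taxa.

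- **Screen.** ALDeX2 is used "to test for relationships between specific bacterial taxa and HPV infection and cervical dysplasia in addition to other clinical variables at each time point". The tests are run visit by visit, and HPV infection is one of several selection variables.
- **Follow-up.** "Taxa thus identified will be examined for changes in relative abundance across time using mixed-effects models to control for multiple measures on each subject", and the sentence goes on: "and comparing to HPV infection status, HPV type and other clinical and HIV correlates".

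The section gives no significance level, selection threshold, number of taxa, multiplicity correction, participant split, outside cohort or whole-procedure permutation for these steps. It does not say that both steps use the same samples, but it names no others, and the per-visit samples are the repeated measures that the mixed models need. The scale on which abundance is modelled in the second step is not stated.

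On the visit structure, the Summary says "Subjects will participate in up to 3 possible study visits over a total of 5 years" and, because time since vaccination varies, "6 possible visit times have been created". The work serves the second exploratory objective.

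**The concern.** A taxon unrelated to HPV reaches the second step only if, at one visit or more, chance made it look related to HPV. The pooled HPV estimate in the mixed model is built partly from that same visit, so it starts off displaced from zero. Its p-value no longer has a 5% chance of falling below 0.05. For the same reason, a false discovery rate procedure applied only to the selected taxa would start from null p-values that are already too small.

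At stake is how the results will be read. A taxon significant at a visit and again in a longitudinal model looks like a finding that was repeated and held up. Section 1.0 (Background, item 6) says the microbiome work will support future risk profiling for cervical cancer, and Section 18.0 plans publication. Apparent corroboration of chance findings would carry weight there.

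**Working it through.** The plan gives no figure to reproduce for this analysis, so the check asks how large the effect could be.

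**Inputs from the documents**
- Six possible visit times and up to three visits per woman (Summary).
- "Four hundred and seven (407) HIV-positive girls and women" offered participation (Section 5.0), and 94% still engaged (Section 4.0, Rationale): 407 × 0.94 ≈ 382. A run with 200 was added.
- Oncogenic HPV in 29% at screening in the parent study (Section 1.0, item 10). A run at 60% was added.

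**Assumptions not in the documents**
- Each visit-level test at 0.05; 150 taxa.
- Three consecutive annual visits per woman, staggered over the six times.
- Within-woman correlation of abundance 0.1 to 0.7, and of HPV status 0.2 to 0.9.
- A Welch t-test on a Gaussian, log-ratio-like abundance as a stand-in for ALDeX2.

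**Step 1: chance that a null taxon is picked.** With independent tests at six visits, 1 − 0.95⁶ = 0.265.

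**Step 2: HPV test in a random-intercept model (time, HPV) on the same samples.** All taxa are null. The joint rate is the product of the two preceding columns.

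| Setting | Null taxa picked | p<0.05 among those picked | Joint |
|---|---|---|---|
| n=382, 3 visits, abundance corr. 0.4, HPV corr. 0.5 | 39.6/150 = 26.4% | 12.0% | 3.2% |
| HPV corr. 0.2 | 39.7/150 = 26.5% | 11.2% | 3.0% |
| HPV corr. 0.9 | 39.0/150 = 26.0% | 13.6% | 3.5% |
| Abundance corr. 0.1 | 40.0/150 = 26.7% | 12.8% | 3.4% |
| Abundance corr. 0.7 | 38.9/150 = 25.9% | 8.4% | 2.2% |
| n=200 | 39.1/150 = 26.1% | 11.9% | 3.1% |
| 2 visits per woman | 40.8/150 = 27.2% | 11.3% | 3.1% |
| HPV prevalence 60% | 39.4/150 = 26.3% | 11.5% | 3.0% |

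A repeat of this layout gave 26-28% picked and 8-14% of those below 0.05. If HPV status never changes within a woman, a further run gave 14-17%. Fitted to every taxon without selection, the same model rejected in 4.8-5.2% of cases in these settings, so selection is the cause.

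**Where the effect is and is not**
- HPV-by-time interaction, picked taxa: 8-12%, also inflated.
- Time trend, picked taxa: 4.6-5.5%, not inflated.
- HPV test on taxa picked only for dysplasia: 4.9-5.9%, essentially nominal.

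**Sensitivity to the visit layout.** If all women shared the same three visits (150 women, abundance correlation 0.3-0.5), independence gives 1 − 0.95³ = 0.143. Simulation gives 13-14% picked, of which 17-23% reach p<0.05. Joint: 14% × 17% = 2.4% to 13% × 23% = 3.0%. Fewer visits mean fewer null taxa picked, but each visit weighs more in the pooled test.

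**Does false discovery rate control at the screen help?** With 20 of 150 taxa truly associated, a 5% rule at each visit carries forward 3.9 of 130 null taxa (3.0%), of which 23% reach p<0.05. A 10% rule carries forward 9.1 of 130 (7.0%), of which 20% do. Fewer null taxa pass, but those that do are further from a valid test.

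**Check of repairs.** Selecting in one half of the women and testing in the other half gave 5.1%.

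**The case against.** The strongest reply is that requiring both steps is stricter than it looks. Only about 2-4% of all null taxa pass the screen and then reach p<0.05, whereas one unadjusted mixed model on every taxon would flag about 5%. This stands. A reader might infer that the two-step plan produces more false declarations than a simple one-step analysis. It does not, in any setting run. What is lost is valid error control within the selected set, and the second result's value as corroboration.

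A second reply is that the work is labelled exploratory, that selected taxa are to be examined rather than confirmed, and that no rule based on a p-value is written down. This also stands, and it keeps the point minor. It does not remove it: the section does speak of testing, and nothing tells a reader that the second-stage HPV p-values need discounting.

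Two wider readings are tempting, and the documents do not support them.

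- **That all longitudinal p-values are too small.** The part of the plan about change over time is not affected. Selection also uses dysplasia and other variables, and a taxon picked on one of those is not noticeably biased for HPV. The clustering and diversity analyses in the same section are not described as passing through this screen.
- **That the second step goes back to raw proportions after a compositional first step.** The plan names relative abundance as the quantity of interest but does not state the model scale, so this cannot be asserted.

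**Conclusion.** The point holds in a limited form. For taxa selected on HPV, the second-stage HPV p-values (main effect and interaction with time) are too small, and a multiplicity correction confined to the selected taxa would not be valid. The same reasoning applies to dysplasia or any other variable used both to select and to retest.

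Under the staggered visit structure in the Summary, the false-positive rate among selected null taxa is about 8-14%, or 1.6 to 2.8 times the nominal 5%. It would be 17-23% if all women shared the same three visits. The direction follows from selecting and retesting on the same variable in the same samples. The size rests on the assumed 0.05 screen, HPV prevalence, correlations and visit layout, and on a t-test standing in for ALDeX2. That both steps use the same samples is inferred from the absence of any other.

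This is a minor point confined to the second exploratory objective. The primary and secondary objectives are untouched.

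**What to change.** Fit the longitudinal mixed model once to every taxon that passes a prevalence filter set without reference to HPV or outcome. Include a participant random effect, time and HPV status, and state a log-ratio scale consistent with the first step. Apply Benjamini-Hochberg control across all taxa tested, and treat other variables of interest in the same way. Keep the visit-by-visit ALDeX2 results as description.

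If the two-step layout is preferred, report the second step as estimates without p-values.

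The cost is a change of SAP wording and somewhat more computing, with no new samples or visits. Fewer taxa will probably be declared. That would come from the false discovery rate control, not from dropping the screen.
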